7.5 Regulatory Reporting of Serious Adverse Events

In the event of a fatal or life-threatening SAE, [name] will notify the FDA by telephone or facsimile within seven calendar days of receipt of the report. [name]. will follow all 7-day alert reports with a written IND safety report within 15 calendar days of receipt of the case.

Serious adverse event cases that concern non-fatal, non-life-threatening events which are unexpected and at least possibly related to the study product will be submitted in writing to the FDA as 15-day IND safety reports within 15 calendar days of receipt.

[name] will require Investigators to obtain follow-up information on all SAEs.

7.6 Unblinding of Study Treatment Assignment

If during the course of the blinded portion of this study a medical emergency requires knowledge of a subject's treatment assignment, the study blind may be broken by authorized persons for that specific subject.

7.7 Pregnancy

If a woman becomes pregnant while on study, this should be reported immediately to the Investigator and the Medical Monitor. All pregnancies will be recorded as an AE and will be followed for outcome.

8 GENERAL ADMINISTRATIVE PROCEDURES

8.1 Protocol Modifications

Protocol modifications will be avoided to the extent possible. Potential modifications include (but are not limited to) refinement of counseling strategies and recruitment techniques, revision of questionnaires and other subject-related documents, and refinement of intervention. Any protocol modification must be approved by [name]. prior to implementation. Protocol amendments will be submitted to the IRB as indicated, depending upon the nature of the modification.

8.2 Clinical Monitoring

There will be no independent data monitoring committee for this Phase 3 study.

The Medical Monitor and Principal Investigator will regularly review the safety data throughout the course of the study.

8.3 Individual Stopping Rules

Any subject with an SAE, whether or not considered related to the study product or procedures, will be discontinued from further study treatment.

8.4 Study Suspension or Termination

As stated above, any SAE must be reported by the Investigator or designee to [name]. and the Medical Monitor. The study will be suspended if two or more SAEs considered "Possibly" or "Probably" related to the product are reported in any study of LACTIN-V. The study will only be resumed if the Medical Monitor and the FDA agree to do so. Study suspension or termination will be reported to the University of Washington IRB.

8.5 Roles and Responsibilities of the Study Site

The study site has the following responsibilities:

- Complete the site University of Washington IRB application.

- Complete the following prior to study start: signature(s) on any applicable clinical trial agreements, FDA forms, financial disclosures, debarment certifications and protocol signature page; CVs and medical licenses (if applicable) of all Investigators; and, if applicable, recruitment materials and laboratory documentation.
- Conduct the study under procedures defined by GCP (Good Clinical Practices).
- Report all new or updated SAE information promptly to [name]. and the University of Washington's IRB within 24 hours of first knowledge.
- Report any instances of unintentional unblinding immediately to [name].
- Submit all significant protocol deviations promptly to University of Washington's IRB
- Resolve all queries regarding the data that arise in the course of the study..
- Provide clinical laboratory services where required by the protocol.
- Obtain annual approval from University of Washington's IRB.
- Complete monthly update and submit to [name]. in report form on the first business day of each month during the study.
- Submit all Expedited Safety Reports and Investigator Letters to University of Washington's IRB within three business days of receipt.

8.6 Protocol Deviations

All significant protocol deviations that the Investigator or site staff believes are of major importance (for example, incorrect randomizations, subject enrolled but not eligible) should be reported to [name]. as soon as possible. Significant protocol deviations may include the following:

- Deviations from the Inclusion/Exclusion criteria that may affect subject safety.
- Deviations (omission or delay) of safety monitoring procedures.
- Deviations in the administration of study product.
- Deviations in obtaining informed consent.

Significant protocol deviations will be reported to the University of Washington IRB, and will also be recorded on the CRF using the Significant Protocol Deviation page. These forms will be completed and faxed to the IRB.

All protocol deviations occurring at each site that are not recorded on these forms will be listed in the Protocol Deviation Log, which will be routinely reviewed by the principal investigator.

9 DATA MANAGEMENT

9.1 Data Collection and Entry

Case Report Forms (CRFs) will be completed at the study site with only the subject identification (Subject ID), which consists of a 2-digit site number and a 4-digit randomization number (the Subject Number). CRF's will be forwarded to the University of Washington for entry onto datasets using Teleform scanning software (Cardiff Software, Inc.). These datasets will be transferred electronically to the study statistician, who will manage and analyze the data. At several points during the project, the data will be examined for out-of-range values, missing data and logical inconsistencies, and adjustments will be made as needed. Final analysis files will be created at the conclusion of data collection and clean-up. Once the last subject has completed Visit 6 and data are cleaned, all analyses will be performed on the data sets through Visit 6. Data will be managed and analyzed using a combination of local and centralized computing resources at the University of Washington. SAS will be used for data management.

10 STATISTICAL CONSIDERATIONS

10.1 Primary Endpoint

The primary endpoint of this Phase 2 study is to evaluate the efficacy of *Lactobacillus crispatus* strain CTV-05 (LACTIN-V) in pre-menopausal women who have a history of recurrent uncomplicated UTI when the product is administered vaginally at a dose of 2 x 10⁹ CFU/capsule once per day for five consecutive days followed by once per week for 10 weeks. The main analysis of interest will be the comparison of UTI during the follow-up period, looking at:

1. UTI incidence over the 16-week study period in the LACTIN-V treatment group (Group A) as compared to the placebo group (Group B) of:
 - a. Symptomatic or Probable UTI
 - b. Symptomatic UTI
2. Time to recurrence, as measured from date of the Randomization Visit (Day 1) to the date of first UTI diagnosis post-randomization, in the LACTIN-V group (Group A) compared to the placebo group (Group B) of:
 - a. Symptomatic or Probable UTI
 - b. Symptomatic UTI
3. Comparison of the number (%) of subjects over the 16-week study period with at least one:
 - a. Symptomatic or Probable UTI
 - b. Symptomatic UTI

10.2 Secondary Endpoints

The secondary endpoints of this study are parameters of vaginal environment and colonization and adverse events due to the study product.

1. Vaginal colonization with total lactobacilli (as assessed by vaginal culture) and *Lactobacillus crispatus* strain CTV-05 (as assessed by rep-PCR) at Visits 1 through 6 in the LACTIN-V group (Group A) as compared to the placebo group (Group B).
2. Vaginal colonization with *E. coli*, in the LACTIN-V group (Group A) as compared to the placebo group (Group B), as assessed by the presence of *E. coli* on vaginal culture at Visits 1 through 6.
3. Shifts in the vaginal microbiota of individual subjects, as assessed by Nugent score of vaginal gram stains at Visits 1 through 6, in the LACTIN-V group (Group A) as compared to the placebo group (Group B).
4. Shifts in the composition of vaginal microbiota, as assessed by qualitative and/or quantitative DNA amplification of stored vaginal specimens from all visits.
5. Presence and/or quantitation of H₂O₂, lactic acid, and cytokine profiles at Visits 1 through 6, in the LACTIN-V group (Group A) as compared to the placebo group (Group B).
6. Safety and tolerability will be evaluated by the number (%) of subjects with any treatment emergent adverse event, reported symptoms and/or abnormal pelvic examination results over the four-month study period.

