For Protocol No. LV-003, 111 of 149 subjects (74.5%) reported at least one AE (76.7% of LACTIN-V subjects and 72.4% of placebo control substance subjects). Overall, the most common AEs reported were vaginal discharge (38.9%), vaginitis bacterial NOS (24.2%), genital pruritis female (23.5%) and vaginal odour (22.1%). Adverse events were mostly mild (67.8%) or moderate (28.2%) in severity, and the majority of subjects had AEs that were assessed as possibly or probably related to study product (56.4%). No safety signal was observed for the LACTIN-V group in regard to AEs, with the exception of a higher rate ($\geq 5\%$ difference between treatment groups) of nausea, diarrhea, dysuria, vaginal discharge and vaginal odour. One subject experienced three simultaneous SAEs (hemiparesis, blurred vision in right eye and headache); however, as this subject was in the placebo control substance group, the SAEs were unrelated to LACTIN-V. Two subjects in the LACTIN-V group discontinued study treatment due to AEs; one subject became pregnant and the other reported nausea and diarrhea, which required treatment. No deaths were reported during this study.

LACTIN-V study LV-004

A conducted by Osel Inc. was planned to involve 100 women with a history of recurrent, uncomplicated UTIs who had recently been treated for UTI with a course of antibiotics. Only subjects treated with amoxicillin/clavulanate (Augmentin), a quinolone or nitrofurantoin would have been eligible for enrollment. Subjects were to be randomized to one of two groups (50 subjects per group) to either receive one capsule of LACTIN-V Formulation 1 (at 5×10^8 cfu/capsule) or one placebo daily for five days followed by one capsule per week for 10 weeks. In addition to safety, this study was to evaluate the preliminary efficacy of LACTIN-V in reducing the incidence of symptomatic, probable and asymptomatic UTI. Subjects were to be queried at each clinic visit for urinary symptoms, including dysuria, frequency, urgency, hematuria, flank pain or suprapubic pain. This study was to also evaluate vaginal colonization with lactobacilli, *Lactobacillus crispatus*, strain CTV-05 and *E. coli* following administration of LACTIN-V.

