3.3 Case Definitions

3.3.1 Symptomatic UTI

Symptomatic UTI is defined as an episode with one or more UTI symptoms (dysuria, urgency, frequency) prompting evaluation and treatment, with a positive urine culture. A positive urine culture is defined as $\geq 10^2$ /ml of an uropathogen in these patients.

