At Visit 1, each subject who continues to meet all inclusion and exclusion criteria will be randomized and will receive a box containing 15 applicators. Two extra applicators will be kept at the study site in case a lost or damaged applicator needs to be replaced. The first study applicator will be inserted under supervision in clinic at this visit. The remaining 14 applicators will be inserted daily at bedtime on Days 2–5, and then weekly. Women are to abstain from sexual intercourse and tampon use for 24 hours after each applicator is used. If the subject's partner uses condoms, they will be instructed to use non-spermicidal condoms to avoid killing the *L. crispatus*. The use of other intravaginal products including douching is prohibited throughout the four-month study period. Subjects must agree not to self-medicate with antibiotics or antifungals during the four-month study period. However, subjects may be treated for any on-study vaginal or other infection if a health care provider deems such treatment necessary. Subjects who receive antibiotic or antifungal treatment after commencing the study should continue to insert the study applicator according to their allocated schedule.

Subjects will be provided with a Study Diary to use to record applicator use information during the study. The Study Diary will also be used by subjects to record any symptoms. Subjects will be instructed on how to use these memory aids to remind them to insert the applicator on the designated day and to record the date and time when each applicator was inserted.

Self-reported symptoms will be evaluated at all study visits. Subjects will be queried about the following symptoms:

Nausea or vomiting
Abdominal Discomfort
Diarrhea
Constipation
Rash
Abnormal Vaginal Discharge/Bleeding
Abnormal Vaginal Odor
Genital itching or burning
External genital irritation/swelling
Painful Urination
Urinary Frequency
Urinary Urgency
Blood in urine

Headache
Other: _____

Other: _____

Subjects will be instructed to call the study clinic if they have any unexpected symptoms at any time during the study.

Pelvic examinations will be performed at all visits to evaluate the external genitalia; cervix and vaginal mucosa for signs of irritation at Visits 1 and 6 and if clinically indicated.

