In addition to safety, this study will evaluate the efficacy of LACTIN-V in reducing the incidence of Symptomatic UTI. Subjects will be queried at each clinic visit for urinary symptoms, including dysuria, frequency, urgency, hematuria, flank pain or suprapubic pain. Urinary dipstick, urinalysis and urine culture will be performed at each clinic visit. Subjects will be asked to return to clinic as soon as possible if they develop symptoms of UTI during the four-month study period.

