6.3.6 Additional Unscheduled Visits

Subjects will be instructed to return to the site if they experience symptoms of UTI during the four-month study period, or to report an adverse event that requires further evaluation.

The following list of procedures and assessments for the Unscheduled Visits is a guide only. The components of the history and physical examination conducted at this visit will be determined by the Investigator or his/her designee. All history and physical data from this visit should be recorded on the Symptomatic Visit CRF:

1. Focused physical examination, if indicated for assessment of symptoms.
2. Pelvic examination, if indicated for assessment of symptoms. A pelvic examination should be performed for all vaginitis symptoms and should be conducted as follows:
 - a. Examination of the external genitalia.
 - b. Speculum insertion and examination of vagina, fornices and cervix with naked eye. Only water must be used to lubricate the speculum at all study visits. Other lubricants could kill *L. crispatus*.
 - c. Vaginal swab for pH, wet mount, KOH, clue cells and amine test (whiff test) performed in clinic.
 - d. Swab of vaginal fluid to be stored for assessment of vaginal microbiota by DNA amplification.
3. Clean catch urine collection for dipstick, urinalysis, and/or urine culture with susceptibility testing if indicated. Urine testing should be conducted for all urinary symptoms while on study.
4. All diagnoses of UTI are to be recorded on the UTI CRF. Subjects diagnosed with UTI during study participation are to be treated as clinically indicated and should continue to receive study treatment.

If the subject has a new symptom (or increase in the severity of an existing symptom), the AE CRF and if necessary, the SAE CRF, should be completed.

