10.10.2 Vaginal Colonization with Lactobacilli

Total lactobacilli (based on culture) will be scored as 1+, 2+, 3+, or 4+.

Colonization with *L. crispatus* strain CTV-05 (based on rep-PCR) will be scored as present or absent (frequency). Number and percent of subjects with positive CTV-05 in each treatment group will be presented. 95% confidence intervals will be calculated to evaluate any difference between the treatment groups.

The differences of these scores between Visit 1 (Day 1, Baseline) and Visits 3 and 6 for each subject will be evaluated within each group and between treatment groups.

10.10.3 *E. coli* Vaginal Colonization

The number (%) subjects with *E. coli* colonization in each treatment group will be summarized by treatment group and visit. 95% confidence intervals will be calculated to evaluate any difference between the treatment groups at a given visit.

10.10.4 Change in Vaginal Microbiota, as assessed by DNA amplification.

The number (%) of specific *Lactobacillus spp.* and uropathogens will be summarized by treatment group and visit. 95% confidence intervals will be calculated to evaluate any difference between the treatment groups at a given visit.

10.10.5 Safety and Tolerability.

The safety endpoints include specific solicited adverse events (AEs), all other reported AEs, serious adverse events (SAEs) and signs of irritation on pelvic examination. The adverse events emerging during the study, their severity and relation to study product will be recorded. Each event will be coded with system organ class and preferred term based on the Medical Dictionary for Regulatory Activities (MedDRA). Number (%) of subjects with AEs will be summarized by system organ class, preferred terms, and treatment group. Severity of AEs and relationship to study product will also be summarized by system organ class, preferred terms, and treatment group. SAEs and reasons for premature termination from study will be summarized by treatment group in frequency and percent. In addition, signs of irritation of the external genitalia, vagina or cervix from pelvic examination, along with their severity and relation to study product will be summarized by treatment group. Furthermore, symptoms and physical findings will be summarized.

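### Urinary symptoms are counted for safety with no split by UTI episode, so if LACTIN-V reduces UTI the unattributed counts could obscure urinary irritation caused by the product

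*Combined protocol and SAP*

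**What the plan says.** **Safety side.** Section 5.1 lists the symptoms asked about at all visits, among them "Painful Urination", urinary frequency, urinary urgency and blood in urine. Section 10.2, item 6, takes as its measure the "number (%) of subjects with any treatment emergent adverse event, reported symptoms and/or abnormal pelvic examination results" over four months. Section 10.10.5 adds: "The safety endpoints include specific solicited adverse events (AEs), all other reported AEs", together with SAEs and signs of irritation, and also promises a summary of symptoms. Table 1 allows Fisher's exact test for selected AE terms or symptoms.

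**Efficacy side.** Section 3.3.1 defines Symptomatic UTI by "one or more UTI symptoms (dysuria, urgency, frequency) prompting evaluation and treatment", plus a positive culture. Section 3.3.2 uses the same symptoms for Probable UTI and does not require a culture. Hematuria is not in either definition, but Section 5.1 asks about urinary symptoms for efficacy "including dysuria, frequency, urgency, hematuria, flank pain or suprapubic pain".

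**Recording.** A visit for UTI symptoms can feed both sides. Under Section 6.3.6 the diagnosis goes on the UTI CRF, and "If the subject has a new symptom (or increase in the severity of an existing symptom), the AE CRF" is completed as well. Section 7.1.1 requires every AE to be recorded, related or not.

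**What is absent.** No section excludes, flags or separately tabulates urinary symptoms that belong to a UTI episode.

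**The concern.** The trial aims to reduce the condition that produces these symptoms. If LACTIN-V works, placebo women will have more dysuria, frequency and urgency from UTI. That surplus offsets any such symptoms caused by the product, and a simple count by arm could show no difference, or a difference favouring LACTIN-V, while irritation is present.

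The plan's own history makes this worth checking. For LV-003, Section 2.2.2.2 reports: "No safety signal was observed for the LACTIN-V group in regard to AEs, with the exception of a higher rate" (a difference of at least 5 percentage points) of five events. Dysuria is the only urinary one among them. At stake is secondary objective 6, the safety of LACTIN-V over four months, in the scenario where efficacy is shown and the tolerability statement carries most weight.

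**Working it through.** **Inputs**
- Planned recurrence: placebo pc = 0.40, LACTIN-V pt = 0.20 (Section 10.4: 40% and a 50% reduction).
- Phase 2 recurrence: pc = 13/48 = 0.271, pt = 7/48 = 0.146 (Section 2.2.2.2, UW/LB-001).
- s, the share of UTIs that bring dysuria: not given; assumed 0.5 to 1.0.
- b, the rate of non-UTI urinary symptoms: not given; assumed 0 to 0.20.

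**The plan's own figure.** Section 10.4 claims more than 80% power with 250 women. With 125 per arm and two-sided alpha 0.05 (assumed; none is stated), z = [0.20·√125 − 1.96·√(2·0.3·0.7)] / √(0.4·0.6 + 0.2·0.8) = 0.966/0.632 = 1.53, a power of 93.7%. The claim is consistent, and this point disputes no figure in the plan.

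**Dysuria alone, no background.** Let x be the rate of product-caused dysuria among LACTIN-V women without UTI dysuria. The arms show equal dysuria when s·pc = s·pt + (1 − s·pt)·x, so x = s(pc − pt)/(1 − s·pt).

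| s | Planned 40% vs 20% | Phase 2 27.1% vs 14.6% |
|---|---|---|
| 0.5 | 0.10/0.90 = 11.1% | 0.0625/0.927 = 6.7% |
| 0.8 | 0.16/0.84 = 19.0% | 0.100/0.883 = 11.3% |
| 1.0 | 0.20/0.80 = 25.0% | 0.125/0.854 = 14.6% |

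Below these values LACTIN-V shows less dysuria than placebo. For example, at s = 0.8 and a true x of 10% under the planned rates, LACTIN-V shows 1 − 0.84·0.90 = 24.4% and placebo 0.8·0.40 = 32%. If pc = pt, then x = 0 and nothing is masked.

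**Any urinary symptom, with background.** Every recurrence is symptomatic by definition, so the rate per arm is p + (1 − p)·(non-UTI rate). The break-even excess is (pc − pt)(1 − b)/(1 − pt). For b = 0, 5%, 10% and 20% it is 25.0, 23.8, 22.5 and 20.0 points at the planned rates, and 14.6, 13.9, 13.2 and 11.7 points at the phase 2 rates.

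**What a split would show.** Take 40% vs 20%, b = 5% and a true 10-point excess among UTI-free women.
- Pooled: placebo 0.40 + 0.60·0.05 = 43%; LACTIN-V 0.20 + 0.80·0.15 = 32%. LACTIN-V looks 11 points better.
- UTI-free women with symptoms, per randomized woman: placebo 0.60·0.05 = 3%; LACTIN-V 0.80·0.15 = 12%. The excess is visible, with about 77% power at 125 per arm (same assumed alpha).
- With no product effect, the second count would be 0.60·0.05 = 3% vs 0.80·0.05 = 4%. The split thus leans slightly against the arm with fewer UTIs, which is why a person-time version is needed beside it.

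**The case against.** **Relatedness is assessed and tabulated.** Section 7.1.3 has the investigator consider the underlying disease as an alternative cause, and Section 10.10.5 tabulates relationship by preferred term and arm. The lead-in to Section 10.2 speaks of "adverse events due to the study product". This stands in part: irritation could still appear in the relatedness table, and a reader who inferred that the plan has no safeguard would be wrong. But the table rests on judgment in women for whom UTI is a ready explanation, item 6 itself carries no relatedness limit, and the table does not clearly cover the separate symptom summary.

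**Baseline symptoms are handled.** One might infer that symptoms left from the entry UTI contaminate the AE counts. They should not: Section 6.3.4 records baseline symptoms, Section 7.1 treats earlier onset as pre-existing unless it increases, and Section 6.3.6 asks for new or worse symptoms. Only the reported-symptoms summary lacks an explicit rule.

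**The prior evidence is mixed.** LV-003 enrolled women with BV. In LV-006, also in BV, dysuria was reported at 21% but AEs overall were evenly distributed between arms. In UW/LB-001, the predecessor in recurrent UTI, AEs were 56% on LACTIN-V vs 50% on placebo, and the commonest were not urinary. Product-caused dysuria is a possibility to check, not an established effect.

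**Safety analysis is descriptive, and the data exist.** Urine is cultured at each clinic visit and UTI diagnoses have their own CRF, so the split could be made later. That shows the remedy is cheap; it does not mean that it is planned.

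**Conclusion.** The point holds in a limited form. As planned, the unattributed urinary-symptom and AE counts depend on efficacy and could obscure product-caused irritation if UTI falls. For dysuria alone with no background, the masked rate is about 11% to 25% at the design effect and about 7% to 15% at the phase 2 rates. Both ranges rest on the assumed share of UTIs with dysuria (50% to 100%).

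A reader might go further and infer that irritation would be hidden throughout the safety analysis. The documents do not support that: masking needs a real UTI reduction, and the relatedness table may still show the signal. Nor do these percentages apply to the composite in Section 10.2, which also takes in all other AEs and pelvic findings. If LV-003's 72.4% placebo AE rate is borrowed as its background (an assumption), the break-even for the composite is 0.25·(1 − 0.724), or about 7 points.

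**What to change.** In Section 10.10.5 and Table 1, keep the all-symptom and all-AE tables. Add, by arm and per randomized subject, painful urination, frequency, urgency and blood in urine split into:
- (a) within a culture-confirmed Symptomatic UTI (Section 3.3.1);
- (b) within a treated Probable UTI without a positive culture (Section 3.3.2);
- (c) outside any UTI episode.

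Compare arms for tolerability on (c) and on (b) + (c). Using (c) alone would be a mistake, because product irritation that is treated without a culture meets the Probable UTI definition and would drop out of the safety comparison. Conversely, (b) + (c) may keep some true but uncultured UTIs, so the two should be read together. Give UTI-free person-time rates as a supplement.

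Show the proportion with any AE with and without culture-confirmed UTI episodes, matching AE and UTI CRF entries by date. For the reported-symptoms summary only, state the baseline rule that Section 7.1 already applies to AEs.

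The cost is SAP wording and a few tables, with no new specimens or visits. The CRFs are not among the documents, so whether AE and UTI entries are already linked cannot be seen. The split conditions on UTI status after randomization, so it supplements the all-event tables and does not replace them.
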